## **PRECIS**

TITLE	Tai Chi for Chronic Low Back Pain in Older Adults
INVESTIGATORS	
[name], Principal Investigator Kaiser Permanente Washington Health Research Institute, Seattle
 
[name] Co-Investigator University of Washington, Seattle
 
[name], NP, PhD, Co-Investigator Kaiser Permanente Washington Health Research Institute, Seattle
 
[name], Co-Investigator University of Washington, Seattle

STUDY OBJECTIVES	
This study is designed to determine the feasibility of conducting a full-scale randomized controlled trial (RCT) of Standard Tai Chi, Enhanced Tai Chi, an Attention Control and Usual Medical Care for chronic low back pain in older adults. In addition, we will consider the feasibility of an attention control. By collecting data on recruitment and randomization rates, Tai Chi class and home practice attendance, rate and severity of adverse events and follow-up rates at 12, 26, and 52 weeks as well as observations of acceptability of Tai Chi classes and adequacy of Tai Chi performed, qualitative comments by participants, study staff and the Tai Chi instructor as well as the acceptability of the Attention Control, we will be able to determine the feasibility of the full-scale RCT.

DESIGN AND OUTCOMES	
This is a feasibility RCT designed to test whether conducting an RCT of Tai Chi versus Attention Control versus Usual Medical Care to improve chronic low back pain in older adults is realistic. The feasibility of the full-scale study will be determined by assessing the feasibility of recruitment; acceptability and adherence of Tai Chi classes and home practice as well as the Attention Control; rate and severity of adverse events and adequate follow-up rates. Outcome measures for studies of back pain, including impact on back-related function and pain – primary outcomes for any RCTs of back pain, will be collected.

POPULATION/SITE	Persons who are at least 65 years of age, have had at least 3 months of non-specific (or degenerative) low back pain (and back pain on at least half the days over a 6 month period), and who rate their pain at least 4 on a 0 to 10 scale and have a score of at least 3 on a 0 to 10 Pain Interference Scale. Participants will be recruited from Kaiser Permanente Washington, an integrated healthcare system in the Puget Sound region of Washington State and from the general population of the region as necessary.
INTERVENTIONS	
Participants will be randomized to one of two treatments:
 
 
• Enhanced Tai Chi (TC)
 
• Comprehensive Health Education Control
 
• Usual Medical Care (UMC)
 

INTERVENTION SCHEDULE	
Enhanced Tai Chi consists of Standard + Maintenance Tai Chi. Standard period: 12 weeks of 2x weekly classes of Tai Chi plus daily home practice on non-class days. Maintenance period: 24 weeks of maintenance Tai Chi (6 weeks of weekly Tai Chi classes; 6 weeks of every other week classes; 12 weeks of monthly classes). Home practice will be encouraged on all non-class days for the entire 52-week follow-up period. Attention Control consists of 12 weeks of 2x weekly classes about senior health with discussion. All Tai Chi participants have access to all care provided by their insurance.
 
Usual Medical Care: participants are free to make any visits to their physicians and other health care providers and use other treatments.

SAMPLE SIZE	78 participants (39 Tai Chi, 15 Attention Control, 24 Usual Medical Care)
RECRUITMENT PERIOD	Participants will be recruited in 2 cohorts of 38 and 40 persons.
STUDY AIMS	
 
1) To determine the feasibility of recruiting and randomizing older adults with cLBP into a trial of Tai Chi versus Attention Control versus Usual Medical Care.
 
2) To determine whether older adults with cLBP will come to classes in the primary 12 week period. To
 

estimate home practice for tai chi (frequency and duration during this period).

- 3) To determine whether older adults with cLBP will come to maintenance classes, practice at home and find benefit from other strategies to enhance home practice.
- 4) To determine the rates of follow-up assessment of older adults with cLBP.

---

#### **FEASIBILITY OUTCOMES**

- 1) Recruitment yield and period of time to recruit and randomize one class cohort. Number of cohorts that could be recruited.
- 2) Class attendance and home practice adherence in primary treatment period
- 3) Class attendance and home practice adherence in secondary treatment period
- 4) Follow-up rates at 12, 26, and 52 weeks for outcome assessment. Primary outcome measures are back-related dysfunction and pain.

---

These outcomes will be measured at baseline, 12 weeks (at the end of standard classes), 26 (during maintenance classes), and 52 weeks.

---

#### **SAFETY OUTCOMES**

Any adverse events identified during classes, on the follow-up interviews or through other means will be documented and reported on a regular basis to the Data Safety Monitoring Body (DSMB). Serious adverse events will be reported to the DSMB within 7 days. If attributable to the interventions, serious adverse events will also be reported to the IRB within 7 days.

---

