#### **7.1 Methods and Timing for Assessing, Recording, and Analyzing Safety Parameters**

We will collect data on adverse events from several sources and incorporate them into a database. These sources are: 1) reports from the Tai Chi instructor(s) of any extraordinary occurrences of concern to them, 2) the questionnaires completed by participants at 12, 26 and 52-weeks will inquire about: any harm they felt from the Tai Chi classes or home practice, and any serious health problems, and 3) participants themselves because the consent form directs participants with injuries they believe may be related to the mind-body programs to call the Principal Investigator, Co-Investigators or the Human Subjects Representative, whose names and phone numbers are listed on the copy of the consent form retained by the participant.

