#### **7.2 Adverse Events and Serious Adverse Events**

We will define an **Adverse Event (AE)** as any unfavorable and unintended diagnosis, symptom, sign (including an abnormal laboratory finding), syndrome or disease which either occurs during the study, having been absent at baseline, or if present at baseline, appears to worsen. Adverse events will be recorded regardless of their relationship to the study intervention.

For this study, **Serious Adverse Events (SAE)** are defined as any research-related event (occurring at any dose or level of intervention) that results in any of the following outcomes:

- Death;

- Life-threatening event;
- Inpatient hospitalization or prolongation of existing hospitalization;
- A persistent or significant disability/incapacity; OR
- Any event that when based upon appropriate medical judgment may jeopardize the health or well-being of the subject and may require medical or surgical intervention to prevent one of the outcomes listed in this definition.

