To assess safety, we will compute the proportion of persons reporting adverse events as well as the type and seriousness of the event. In our prior studies, 15 to 29% of participants reported mild transient increases in pain when stretching or doing yoga. We think adverse events for Tai Chi may be similarly mild, but slightly less common because of the nature of the movement.

To assess follow-up rates, we will compute treatment specific and overall follow-up rates at each time point. While our prior trials have consistently had post-treatment follow-up rates over 90% in the short term and close to that at one-year follow-ups, we will consider follow-up rates of 80% or better to indicate feasibility.

As described in Section 6.2.4iii, we will obtain qualitative feedback on all aspects of the study from 30 participants. Our prior experience suggests this number is sufficient to elicit a broad range of experience and to begin to see themes and experiences repeated across respondents (i.e., achieve "response saturation"). [name], an experienced qualitative researcher, will conduct these discussion groups, which will be audio recorded and transcribed. We will also invite suggestions for improvement in the study procedures and protocols. Because these debriefing interviews will inquire

about specific experiences and suggestions for improving our procedures and protocols, our analyses will be largely descriptive and not require resource-intensive ethnographic analysis techniques.

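### The single all-source adverse-event proportion tilts toward Tai Chi if it is read by arm: scheduled classes number 36, 24 and none, and no split by source is planned

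*Protocol*

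**What the plan says.** **Sources.** The Precis (Safety Outcomes) covers every route: "Any adverse events identified during classes, on the follow-up interviews or through other means will be documented and reported on a regular basis". Section 7.1 adds: "We will collect data on adverse events from several sources and incorporate them into a database". It names three sources:

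- "reports from the Tai Chi instructor(s) of any extraordinary occurrences of concern to them";
- questionnaires at 12, 26 and 52 weeks, asking about "any harm they felt from the Tai Chi classes or home practice, and any serious health problems";
- calls from participants who think an injury came from the mind-body programs.

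Table 4 (Schedule of Evaluations) marks adverse events in the class column, which covers both Tai Chi and Attention Control, as well as at the follow-up visits.

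**Definition.** Section 7.2: "Adverse events will be recorded regardless of their relationship to the study intervention".

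**Analysis.** In Section 9.6 i, "we will compute the proportion of persons reporting adverse events as well as the type and seriousness of the event". The SAP repeats this. Neither document limits the proportion to a common source or tabulates events by source.

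**Class schedule.** Precis: "Standard period: 12 weeks of 2x weekly classes of Tai Chi plus daily home practice on non-class days". Section 5.1.3 adds the tapered maintenance classes. Section 5.3 gives Attention Control two classes a week for 12 weeks. Section 5.2 gives Usual Medical Care no classes.

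**The concern.** How often an event is recorded depends on how often someone is placed to notice it, and that differs by arm. Tai Chi classes after the first open with a check-in (Section 5.1.2), a staff member observes each class (Section 5.1.6 iii), and a missed class prompts a call (Section 5.1.6 ii). Usual Medical Care has no counterpart. Because events count whether or not they are related to the intervention, ordinary illness in people aged 65 and over enters the numerator, and it is more likely to surface where there is more contact.

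The Precis names the rate and severity of adverse events among the grounds for judging whether a full-scale trial is feasible. A reader who sets the Tai Chi proportion beside the Usual Medical Care proportion could take extra observation for extra harm.

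**Working it through.** The plan gives no figure to reproduce for this point. The check is a count of contacts and then an illustration on stated assumptions.

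**1. Scheduled contacts (Precis, Sections 5.1.3, 5.2 and 5.3)**

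- Tai Chi: 12 × 2 = 24 standard classes, plus 6 + 3 + 3 = 12 maintenance classes, giving 36. With three follow-up assessments: 39.
- Attention Control: 12 × 2 = 24 classes. With three assessments: 27.
- Usual Medical Care: no classes, three assessments: 3.

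These are scheduled contacts; actual contacts depend on attendance.

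**2. Illustration of the tilt**

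Let *p* be the true proportion of persons with an event, equal in all arms. Let *q* be the chance that the questionnaires capture it, also equal in all arms. Let *c* be the chance that class contact captures it if it falls in weeks 1 to 36 of 52. Treat the two routes as independent. The documents give none of these rates.

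- Recorded in Tai Chi = *p* × [1 − (1 − *q*)(1 − *c* × 36/52)]
- Recorded in Usual Medical Care = *p* × *q*

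The ratio does not depend on *p*. With *q* from 0.5 to 0.9 and *c* from 0.25 to 0.75:

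- Lowest (*q* = 0.9, *c* = 0.25): *c* × 36/52 = 0.173; 1 − 0.1 × 0.827 = 0.917; ratio 0.917/0.9 = **1.02**.
- Middle (*q* = 0.5, *c* = 0.5): *c* × 36/52 = 0.346; 1 − 0.5 × 0.654 = 0.673; ratio 0.673/0.5 = 1.35. At *p* = 30% this is 20.2% against 15.0%.
- Highest (*q* = 0.5, *c* = 0.75): *c* × 36/52 = 0.519; 1 − 0.5 × 0.481 = 0.760; ratio 0.760/0.5 = **1.52**.

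**3. Sensitivity to the assumptions**

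A second version drops the 36/52 factor and lets *c* run from 0.1 to 0.6 over the whole follow-up, with *p* at the 15% to 29% that Section 9.6 i reports from prior studies. The ratio runs from 1.01 (*q* = 0.9, *c* = 0.1) to 1.60 (*q* = 0.5, *c* = 0.6), and the difference from 0.2 to 8.7 percentage points. For example, *p* = 29%, *q* = 0.7, *c* = 0.3 gives 0.29 × (1 − 0.3 × 0.7) = 22.9% against 0.29 × 0.7 = 20.3%.

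If class contact caught only events that the questionnaires would catch anyway, the ratio would be 1.00.

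**4. What a common source would do**

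With only events elicited at the shared assessments, the class term drops out and every arm has expectation *p* × *q*, ratio 1.00. That needs the same *q* in every arm. The questionnaire in Section 7.1 does not meet this condition: its two items are harm from Tai Chi and serious health problems, so no item described there reaches a non-serious event in Usual Medical Care.

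**The case against.** **No between-arm comparison is written.** Section 9.6 i asks for treatment-specific figures for retention and follow-up but not for adverse events, and the only comparator it names is the rate in prior stretching and yoga studies. The model in Section 9.6 iii concerns outcome measures. This stands. A reader might infer that the plan commits to an invalid between-arm safety comparison; the documents do not say so. Pooling is likewise inferred, from one database and a proportion with no source restriction. What remains is that a three-arm trial's proportion will naturally be read by arm, and that a single all-arm figure would mix unequal surveillance.

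**The contact count overstates observation.** A reader might take 39 against 3 as that many equal chances to be recorded. Section 7.1 describes the class route only as instructor reports of unusual occurrences, not a query at every class, and names no reporter for Attention Control classes. The mark in Table 4 gives no method. Classes are also sparse in the last 18 of the 36 weeks. All this stands, and it argues for the lower end of the range.

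**The control arms are not the only guide to background events.** Relatedness is also judged: the reporting table in Section 7.3 splits serious events by it, and Section 7.4 uses it for following up non-serious ones. This stands, but it does not correct the proportion, which counts events regardless of relationship.

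**The tilt is small against chance.** The middle case is a gap of 5.2 points with standard error √(0.202 × 0.798/39 + 0.150 × 0.850/24) = 0.097, about 10 points. This is true for one pilot read alone. The tilt is systematic all the same, and it can be removed cheaply.

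**Consequences are limited.** Adverse events are absent from the numbered feasibility outcomes, no threshold is set, and the stopping text in Section 9.4 concerns serious events in the Tai Chi arm rather than an excess over control. This also stands.

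**Conclusion.** The point holds as a matter of interpretation and reporting. Events arrive through routes that differ by arm and are summarised as one proportion with no source split. Read by arm, that proportion leans toward more recorded events in Tai Chi when true incidence and questionnaire capture are equal and class contact catches anything the questionnaires miss. The size is not identifiable from the documents: about 1.02 to 1.52 times under the assumed capture rates, and 1.01 to 1.60 under the alternative set.

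A reader might go further and conclude that the trial will report a spurious excess of harm, or that restricting the comparison to the existing follow-up questionnaires would make the arms comparable. Neither is supported. The first depends on capture rates that nobody has stated. The second fails because the harm item in Section 7.1 is itself specific to Tai Chi.

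**What to change.** In Section 9.6 i and in the SAP:

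1. Record the source of each event (class, call or scheduled assessment).
2. Report the all-source proportion by arm as a descriptive safety summary, and show class- and call-identified events by arm and source.
3. Base any between-arm comparison only on events elicited at the 12-, 26- and 52-week assessments by the same neutrally worded adverse-event question put to every arm. For that purpose this question replaces the Tai Chi-specific harm item in Section 7.1.
4. Continue to list and report serious events from all sources as planned.

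The cost is a source field in the existing database, one reworded questionnaire item and a short statement in each document. The comparative proportion would omit some non-serious events found only in class; these stay visible in the separate listing.

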#### **MASKING**

All persons collecting outcome information (i.e., assessors) will be masked to each participant's group assignment.

## **1. STUDY OBJECTIVES**

This study is designed to determine the feasibility of conducting a full-scale randomized controlled trial (RCT) of Standard Tai Chi, Enhanced Tai Chi and Usual Medical Care for chronic low back pain in older adults. In the feasibility study, we will test our ability to recruit and randomize older adults with chronic low back pain, to determine whether the Enhanced Tai Chi intervention is feasible in terms of class attendance and home practice, and to determine follow-up rates at 12, 26 and 52 weeks.

## **2. BACKGROUND AND RATIONALE**

### **2.1 Background on Back Pain**

Back pain is the leading cause of disability worldwide, with both prevalence and burden increasing with age, with an estimated 12% of adults over age 65 suffer from impairing cLBP. In the US, about \$86 billion is spent annually on direct costs of medical care for back/neck pain. Escalating costs of care for back pain are particularly marked for older Americans. While the Medicare population increased only 42% between 1991 and 2002, costs for back pain increased 387%. In addition, during a recent 12-year period Medicare expenditures for epidural steroid injections increased 629%, expenditures for opioids for back pain increased 423%, while the number of lumbar magnetic resonance images increased 307% and the number of spinal fusion surgeries increased 220%. Despite these large investments in medical care for back pain, the health and functional status of persons suffering from back pain in the U.S. has deteriorated. Moreover, the rapid projected growth of older adults ensures that back pain in older adults will assume an increasingly greater clinical burden in the years to come.

Determining the cause of chronic low back pain (cLBP) is often difficult because of the numerous structures in the back that can give rise to pain. Moreover, virtually all older adults have radiographic evidence of spinal osteoarthritis, even though most are asymptomatic. Even among older adults with back pain, the severity of their symptoms is poorly correlated with the severity of the imaging findings. Moderate to severe spinal stenosis is as common in older adults with and without chronic back pain. Thus, imaging is not a good method to discern the cause of back pain in most circumstances.

### **2.2 Study Rationale**

Identifying safe and effective treatments for cLBP in older adults remains a major challenge for clinicians, researchers, payers, and patients. Clinical guidelines for back pain in older adults are not available and many older adults have yet to find adequate relief. Older adults commonly have more disabling back pain, more comorbidities with attendant polypharmacy and are at higher risk of adverse effects of commonly used medication and non-pharmacological treatments. They have substantially increased risks for: 1) gastric bleeding and renal insufficiency from use of NSAID drugs, 2) falls with use of muscle relaxants (which affect the central nervous system), and 3) falls, fractures, and cognitive impairment with use of narcotic analgesics. Because many older adults already take multiple medications for other chronic conditions, using medications for back pain increases their risk of drug-drug interactions. Surgical risks

also increase with age. Safety concerns are not limited to the use of conventional medical care. Even normally low risk complementary and integrative medical treatments such as high velocity spinal manipulation techniques may be contraindicated for older adults with osteoporosis, compression fractures, and other degenerative conditions. This may explain why older adults receive less treatment of any type for their back pain, despite reporting similar pain intensity and more disability.

Given the expected aging of the US population in the coming decades, finding safer treatments for them is imperative. The 2007 back pain guidelines found 8 treatments effective for chronic low back pain. These included exercise programs as well as three mind body therapies (wherein the mind is used to affect physical function and improve health -- yoga, cognitive behavioral therapy, and progressive muscle relaxation. The most effective exercise programs included supervision of participants and encouraged adherence to achieve high dosage. Stretching exercises were found to be best for reducing pain and muscle strengthening exercises were best for improving function. While some mind-body complementary and integrative health treatments such as meditation focus primarily on the mind, others including yoga and Tai Chi, promote movement as well as mental focus.

Tai Chi, a mind-body exercise from China that has grown in popularity in the US, looks to be an excellent candidate as a treatment for chronic low back pain in older adults. Tai Chi has been found effective for younger adults with chronic low back pain. Both studies measured pain intensity and found improvements, while the Hall study also measured back-treatments function and found improvements in it as well. It contains numerous elements that are likely accessible to older adults that may be therapeutic. First, Tai Chi features gentle and progressive stretching movements within a moderate range of motion. It is likely to be relatively safe because it avoids putting the body into full extension or contraction as other exercise and yoga sometimes do. Of roughly 50 RCTs of Tai Chi (mostly of older adults) that monitored adverse effects, none reported any severe adverse effects. Second, Tai Chi focuses on enhancing the body's capacity to integrate core and leg muscles rather than focusing on single muscle groups. Third, Tai Chi includes key characteristics of other exercise programs that have been found effective for cLBP (i.e., stretching and strengthening exercises delivered in supervised programs). Fourth, Tai Chi incorporates focused breathing, mindful attention, visualization, and other components that are known to be beneficial for chronic pain. Fifth, Tai Chi classes provide a venue for personal and social connection for persons who are socially isolated. Finally, baby boomers, who are now reaching age 65 in large numbers, have embraced a wide variety of CIM treatments and may be less enthusiastic about participating in the types of exercise programs popular among the preceding generation.

In addition, Tai chi appears to have benefits for numerous health concerns and conditions that are more common in the elderly, including balance and falls prevention, cardiorespiratory fitness, cognitive performance, congestive heart failure, bone health, and osteoarthritis.

In summary, we think Tai Chi is an ideal therapy for cLBP in older adults because it is safe, promotes active engagement in gentle exercise, includes a variety of potentially therapeutic elements, has been found effective for younger adults, and has been found helpful for a variety of comorbidities affecting many older adults. We are unaware of studies evaluating Tai Chi in older adults with chronic back pain. However, our 2001 survey of older adults with back pain in Seattle found that a majority reported interest in Tai Chi training if it were offered for free and was recommended by their physician.

This study is proposed as a feasibility study comparing an “Enhanced Tai Chi” group to “Comprehensive Health Education” to “Usual Medical Care”, which, if successful, would pave the way for a full-scale trial to evaluate Tai Chi as a treatment for older adults with chronic low back pain. Section 2.2a describes this goal, which is important for understanding the context of the feasibility trial, which is further described and justified in Section 3.

